5.4 Subject Disposition

The number of subjects in each analysis population will be presented along with reason for any exclusions. Subject accountability will be summarized by visit. The number of subjects who are enrolled, eligible for follow-up, and number completing clinical follow-up will be summarized for each protocol-required visit. We will also summarize the number and percentage of subjects completing the Trial phase (with and without success), the number of subjects receiving a permanent implant, and the number of subjects with an explant. In addition, the number of subjects who complete the study or exit early will be summarized by reason. The number and percentage of subjects crossing over will be presented by visit.

5.5 Demographics and Baseline Characteristics

Descriptive statistics will be presented for all clinically-relevant baseline demographic, medical history, and clinical characteristic variables.

5.6 Repeated Measures Analyses Methods

For repeated measures models based on assessing measurements over time, estimation will be based on maximum likelihood (for binary data, based on a Laplace approximation). Such methods produce validate estimates when there is missing data that is “missing at random”. A compound-symmetric covariance structure will be used to account for within-subject correlation due to repeated observations on subjects. Time will be treated as a categorical variable. Least-square means estimates will be produced to assess differences between groups at each time point and averaged over the first 6 months.

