#### **B.9.2.4 Handling of Missing Data**

Missing data will be minimized by rigorous follow-up and investigator and site training. Additionally, for subjects in the DTM™ SCS arm who do not have a successful Trial Phase, results from the Trial Phase will be utilized for the primary endpoint as described in Section B.7.2. Effectiveness Assessment Definitions. In case of missing data Mixed Model for Repeated Measures (MMRM) will be used to produce estimates. Additionally, sensitivity analyses for missing data will be performed. Unless otherwise specified, all other analyses will be based on the evaluable data with no imputation.

Details on these analyses will be provided in a separate statistical analysis plan.

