5.7 Analysis of Study Endpoints

5.7.1 Primary Efficacy Endpoint

Pain rating on the 10 cm Visual Analog Scale (VAS) is considered the primary outcome measure. Analysis will be based on the percentage of individual responders, defined as a decrease in back pain VAS by at least 50% at 6 months after Permanent Device Activation (Test group) or 6 months post-randomization (Control group) as compared with Baseline.

Statistical Analysis Plan		Page 9 of 14
Sponsor SGX International	Study EU RCT DTM SCS vs. CMM	Version 3.0

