Missing data will be imputed using the PROC MI procedure in SAS. PROC MI imputes missing covariates in the order variables are listed on the VAR statement. The variables will be listed on the VAR statement in the order listed above. Missing covariates will be imputed using fully conditional specification (FCS) methods. The regression method will be used to impute the missing endpoint values. If necessary to facilitate imputation, an augmented likelihood approach will be used. Explorations to omit predictors may be conducted if the primary effectiveness multiple imputation models will not converge.

For each multiple imputation model, 100 imputed datasets will be generated. The Pearson Chi-square statistic will be computed in each imputed dataset. The Chi-square statistics will be transformed using the Wilson-Hilferty transformation to provide an approximately normal test statistic and standard error. Additionally, the proportions of responders will be estimated for both arms in each imputation. The normalized test statistics and estimated proportions with the associated standard errors will then be combined for inference using standard methods such as those available in SAS PROC MIANALYZE or other valid statistical software.

An additional supporting analysis of the primary endpoint will use likelihood based repeated measures models to produce estimates of the primary endpoint by treatment group and the p-value for a difference between treatment groups in the presence of the missing data.

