The following secondary endpoints do not have an associated hypothesis, and no significance level will be assigned to statistical tests that may be performed.

- Comparison of Back Pain Treatment Success (responder rate), measured as subjects with at least a 50% reduction in Back Pain VAS, between test and control
- Comparison of mean change from Baseline in Back Pain VAS, between test and control.

Repeated measures models will be used to produce estimates for these two secondary endpoints, with graphical presentation of the responder rates and mean changes from baseline.

Analysis of results through 6 months will be based on the mITT population. For time points after 6 months where crossover is allowed, crossover subjects will be counted as failures (i.e. non-responders) for endpoints defined in terms of responders, carrying forward the baseline (pre-treatment). Sensitivity

Statistical Analysis Plan		Page 12 of 14
Sponsor SGX International	Study EU RCT DTM SCS vs. CMM	Version 3.0

analysis of both secondary endpoints will also be performed to where crossover subjects are censored at the point of crossover.

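### The SAP turns a subject-specific binary model into supportive responder rates without averaging over the random effects, so those rates and their difference may be misstated

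*SAP*

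**What the plan says.** SAP 5.6 sets out the repeated-measures method: "estimation will be based on maximum likelihood (for binary data, based on a Laplace approximation"). On correlation it adds: "A compound-symmetric covariance structure will be used to account for within-subject correlation due to repeated observations on subjects". On output: "Least-square means estimates will be produced to assess differences between groups at each time point and averaged over the first 6 months". It does not name the link, the scale on which the least-squares means are presented, or any averaging over the subject effects.

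Two later sections use this model for responder data:

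- SAP 5.7.1.2 describes an additional supporting analysis that "will use likelihood based repeated measures models to produce estimates of the primary endpoint by treatment group", with a p-value for the difference between arms.
- SAP 5.7.2 uses repeated-measures models for the responder-rate and mean-change endpoints that carry no hypothesis, "with graphical presentation of the responder rates and mean changes from baseline".

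The quantity that these outputs are meant to describe is a population percentage. SAP 5.7.1 states: "Analysis will be based on the percentage of individual responders".

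The primary analysis does not use this model. SAP 5.7.1.1 specifies a Pearson chi-square test. If data are missing, SAP 5.7.1.2 replaces it with multiple imputation (MI), in which responder proportions are computed within each imputed dataset.

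**The concern.** A Laplace approximation for binary data approximates an integral over subject-level random effects, so the fitted model is conditional on the subject. With a logit link, the inverse link of a conditional mean is not the mean of the inverse link. A least-squares mean back-transformed at a random effect of zero therefore differs from the arm's responder percentage, and the gap grows with the within-subject correlation. The continuous VAS change does not have this problem, because with an identity link the conditional and marginal means coincide.

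The SAP calls the output an estimate of the primary endpoint and a responder rate, so some back-transformation is implied. The most direct one gives a different quantity. At stake is a supportive estimate and a figure that could show a treatment difference well away from the chi-square or MI result printed beside them. A reader could take the gap as a contradiction, or take the larger figure as the effect.

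**Working it through.** **Inputs.** Planned responder rates of 60% and 30%, two-sided alpha 0.05 and 50 per arm are from SAP section 4 and Protocol B.5.5.1. The rates of 80% and 51% are from the earlier study described in Protocol B.1. The documents give no within-subject correlation. An intraclass correlation (ICC) of 0.2 to 0.8 on the latent logit scale is assumed.

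**The plan's own figure.** The null standard error is √(2 × 0.45 × 0.55 / 50) = 0.0995. The alternative standard error is √((0.60 × 0.40 + 0.30 × 0.70) / 50) = 0.0949. Power = Φ((0.30 − 1.96 × 0.0995) / 0.0949) = Φ(1.11) = 86.6%, and exact enumeration gives 87.6%. The stated power of more than 85% reproduces.

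**Conditional against marginal rates.** Take a random-intercept logistic model with SD s, where ICC = s² / (s² + π²/3). For each arm, solve for the intercept a such that the average of expit(a + sZ) over a standard normal Z equals the planned rate. Then report expit(a), which is what an inverse-linked least-squares mean shows. Results for true rates of 60% and 30% (difference 30 points, odds ratio 3.50):

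| ICC | s | Test | Control | Difference (points) | Conditional odds ratio |
|---|---|---|---|---|---|
| 0.2 | 0.91 | 61.7% | 27.1% | 34.6 | 4.34 |
| 0.3 | 1.19 | 62.7% | 25.4% | 37.3 | 4.94 |
| 0.5 | 1.81 | 65.3% | 21.3% | 44.0 | 6.96 |
| 0.7 | 2.77 | 69.6% | 15.2% | 54.4 | 12.79 |
| 0.8 | 3.63 | 73.5% | 10.7% | 62.8 | 23.08 |

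**Direction.** Conditional probabilities move away from 50%, so the sign of the error depends on the rates. Over the same ICC range:

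- 80% versus 51% (true 29 points): 32.1 rising to 44.2.
- 90% versus 70% (true 20 points): 19.5 falling to 10.2.
- 30% versus 10% (true 20 points): 19.5 falling to 10.2.
- Equal rates, computed at 60% in both arms: 0 throughout.

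**Check with a fitted model.** Laplace maximum-likelihood fits were run on simulated trials at 60% versus 30%, with 50 per arm and 150 trials per setting. The month-6 differences below are means, in points:

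| Visits | ICC | Inverse-linked | Raw | Averaged over random effect |
|---|---|---|---|---|
| 3 | 0.3 | 37.1 | 30.8 | 31.3 |
| 3 | 0.5 | 43.2 | 29.8 | 30.9 |
| 3 | 0.7 | 51.6 | 27.6 | 30.3 |
| 7 | 0.3 | 36.6 | 29.9 | 30.1 |
| 7 | 0.5 | 43.8 | 30.6 | 31.1 |
| 7 | 0.7 | 53.4 | 30.0 | 31.3 |

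The inverse-linked difference exceeded the raw one in 99% to 100% of runs. Averaging the fitted probabilities over the random-effect distribution brought it back to 30 to 31 points.

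**The case against.** The strongest reply is that nothing decisive rests on this model. Study success depends only on the primary superiority test (Protocol B.8.2, Definition of Success), and the chi-square and MI proportions are already marginal. SAP 5.7.1.1 presents the observed numerator, denominator and percentage. Protocol B.7.4 has responder data summarised at each visit from 1 to 24 months. The endpoints in SAP 5.7.2 that use the model carry no hypothesis. All of this stands, and it makes the point minor.

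A second reply is that the SAP does not say the means will be inverse-linked. A contrast left on the logit scale would be a valid conditional comparison, and the plot could show observed rates. That also stands. The defect is an unstated step whose most direct reading gives the wrong quantity.

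Three stronger readings are tempting, and the documents do not support them:

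- **The model always exaggerates the effect.** It does so at 60% versus 30%, but the direction reverses when both rates lie far out on the same side of 50%.
- **Trial Phase failures force the upper end of the range.** SAP 5.7.1.2 repeats their Trial Phase result at every visit, which would raise the correlation. The mITT definition in SAP 5.2 keeps only test subjects who complete that phase successfully. Whether failures enter the model is therefore unresolved. Scoring crossovers as non-responders concerns only visits after month 6.
- **The protocol gives this model the lead role.** Protocol B.9.2.4 says "In case of missing data Mixed Model for Repeated Measures (MMRM) will be used to produce estimates", but it mentions neither binary data nor a Laplace fit, and it leaves details to the SAP. Its mismatch with MI in the SAP is a separate matter to reconcile.

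**Conclusion.** The point holds as a minor one. As written, SAP 5.6 allows subject-specific probabilities to be presented as responder percentages in the supportive primary estimate and in the responder plots. If they are inverse-linked without averaging, a true difference of 30 points at the planned rates would appear as about 35 to 63 points. At other rates it could appear too small.

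The size rests on three assumptions: a logit link, a normal random intercept, and a random-intercept SD of 0.9 to 3.6, which the documents do not give. With no treatment effect the difference stays at zero, so the false-positive rate of the supportive test is not in question. The primary result and the observed percentages are unaffected.

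**What to change.** In SAP 5.6, state the link function and the scale on which least-squares means are reported. In SAP 5.7.1.2 and 5.7.2, report and plot marginal responder percentages by averaging the fitted probabilities over the estimated random-effect distribution, with standard errors to match. Alternatively, plot the observed or MI proportions. Fit the month-6 supportive model to data through month 6 only, as the MI model already does, so that later crossover scoring cannot influence it.

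GEE is also marginal. Fitted to observed data without weighting or MI, however, it would lose the missing-at-random validity on which SAP 5.6 relies. Averaging the existing model keeps that validity, and it keeps the supportive analysis independent of the imputations.

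The cost is a few sentences in the SAP and a few lines of code, with no new data and no change to the sample size. At the planned rates the displayed effect becomes less favourable.

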5.7 Analysis of Study Endpoints

5.7.1 Primary Efficacy Endpoint

Pain rating on the 10 cm Visual Analog Scale (VAS) is considered the primary outcome measure. Analysis will be based on the percentage of individual responders, defined as a decrease in back pain VAS by at least 50% at 6 months after Permanent Device Activation (Test group) or 6 months post-randomization (Control group) as compared with Baseline.

Statistical Analysis Plan		Page 9 of 14
Sponsor SGX International	Study EU RCT DTM SCS vs. CMM	Version 3.0

5.7.1.1 Primary Analysis

The *primary efficacy endpoint* will be evaluated with a Pearson Chi-square binomial test for superiority at the two-sided 0.05 alpha level.

H_0 : The percentage of subjects (P) who achieve a 50% improvement in their back VAS pain score at 6 months in the Test group is the same as in the Control group.

$$P_{\text{Test}} = P_{\text{Control}}$$

H_1 : The percentage of subjects (P) who achieve a 50% improvement in their back VAS pain score at 6 months in the Test group is superior to that in the Control group.

$$P_{\text{Test}} \neq P_{\text{Control}}$$

Primary analysis will be based on the mITT analysis set.

In addition to the results from the hypothesis test, the numerator and denominator and percentage responders will be presented.

5.7.1.2 Handling of Missing Data

For subjects in the DTM™ SCS arm who do experience an unsuccessful Trial Phase, also referred to as a **Trial Failure**, results (i.e., VAS back scores) from the Trial Phase will be utilized for the primary endpoint. Specifically, the Trial Phase results of subjects who failed the Trial Phase will be attributed for each time point throughout the study, as if they remained in the study.

Subjects who did not complete the Trial Phase due to withdrawal (e.g., an adverse event experienced during the Trial Phase, physician withdrawal due to non-compliance, withdrawal of consent, etc.), will not be included in the mITT analysis data set.

In the event of missing primary endpoint data among the mITT subjects either randomized to control or DTM™ SCS subjects who did complete the Trial Phase, the primary analysis for the primary endpoint will be conducted using multiple imputation (MI) methodology rather than the methods specified in Section 5.7.1.1. The specified Pearson Chi-square test will be presented for the observed data as a supporting analysis.

For the MI analysis each missing datum is replaced by multiple values in multiple datasets. The imputed datasets are then analyzed and combined for inference. Since the primary efficacy, and secondary efficacy endpoints, are based on the same underlying data of change in VAS, and vary only in the parameterization (continuous VAS vs. dichotomized responder) or value used for the null hypothesis, the same imputed data sets will be used for the analysis of each endpoint. Imputation will be performed separately by treatment group.

Statistical Analysis Plan		Page 10 of 14
Sponsor SGX International	Study EU RCT DTM SCS vs. CMM	Version 3.0

For each imputation model, covariates will include:

- Baseline variables: age (years), gender, number of year(s) since diagnosed with chronic back pain, unilateral versus bilateral pain, back pain VAS
- Follow-up variables: end of trial phase back pain VAS, follow-up back pain VAS (after device activation) from 1 month through 24 months. The imputation models employed will correspond to the hypothesis being tested, for the primary and secondary endpoints through 6 months, the models will use data through 6 months. For secondary endpoints post 6 months, the model will be extended to the relevant time point.

Missing data will be imputed using the PROC MI procedure in SAS. PROC MI imputes missing covariates in the order variables are listed on the VAR statement. The variables will be listed on the VAR statement in the order listed above. Missing covariates will be imputed using fully conditional specification (FCS) methods. The regression method will be used to impute the missing endpoint values. If necessary to facilitate imputation, an augmented likelihood approach will be used. Explorations to omit predictors may be conducted if the primary effectiveness multiple imputation models will not converge.

For each multiple imputation model, 100 imputed datasets will be generated. The Pearson Chi-square statistic will be computed in each imputed dataset. The Chi-square statistics will be transformed using the Wilson-Hilferty transformation to provide an approximately normal test statistic and standard error. Additionally, the proportions of responders will be estimated for both arms in each imputation. The normalized test statistics and estimated proportions with the associated standard errors will then be combined for inference using standard methods such as those available in SAS PROC MIANALYZE or other valid statistical software.

An additional supporting analysis of the primary endpoint will use likelihood based repeated measures models to produce estimates of the primary endpoint by treatment group and the p-value for a difference between treatment groups in the presence of the missing data.

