### **B.6.6. Test Arm: End of Trial Assessment**

At the end of the Trial Phase, subjects will be assessed for pain intensity under optimal therapy parameters. Anterior-posterior (AP) and lateral X-ray imaging will be done at the end of the Trial Phase. The subject will be assessed for adverse events and medication usage.

Those who have a "successful Trial Phase" (defined as a 50% or greater pain reduction from Baseline in their back pain) will proceed to permanent implantation of the SCS system to evaluate DTM™ SCS therapy, and permanent implantation of the Intellis™ SCS system will be scheduled. A threshold of 50% for the Trial Phase was predetermined as the minimum pain reduction that warrants consideration of a permanent implant and an opportunity to achieve a 50% pain reduction as defined in the Individual Subject Success criterion (see Section B.7.3).

Data from subjects who did not achieve 50% or greater pain reduction in back pain will not receive permanent implantation and will be carried forward toward the primary endpoint. These subjects will have the leads explanted and will exit the study. Following this exit, subjects will be followed by the Investigator at regular intervals, as dictated by standard of care at each site, in order to facilitate pain management. Any additional non-study related monitoring of the subject will be the responsibility of the subject's personal physician, as dictated by reasonable medical care.

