5.2 Analysis Sets

The following analysis sets are defined for analysis:

- Modified Intent to Treat (mITT): All randomized subjects to the test arms who successfully complete the Trial Phase and all successfully randomized subjects to the control arm.
- Intent-to-Treat (ITT): All successfully randomized subjects who met all the enrollment criteria.
- Per-Protocol (PP): All test subjects who received a permanent device implant and all control subjects who contributed their data to the primary and secondary endpoint without any major protocol deviations (that would render their data unevaluable).

The primary analysis of the primary and secondary endpoints will be performed on the mITT population. Supportive analyses will be performed for the Intent-to-Treat and Per-Protocol population.

For secondary endpoint analyses incorporating crossover data (i.e. data gathered in the post 6-month periods), sensitivity analyses will be performed to examine the impact of crossover.

If a supportive analysis set is the same as the mITT set, the results will be the same and will not be regenerated for that supportive analysis set.

Statistical Analysis Plan		Page 8 of 14
Sponsor SGX International	Study EU RCT DTM SCS vs. CMM	Version 3.0

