5.7.2.1 Handling of Missing Data

Since the two secondary endpoints are based on the same underlying VAS data as that for the primary efficacy endpoint, a similar treatment of handling missing data will be applied for the trial phase outcomes. In particular, for subjects who have a successful Trial Phase and planned to receive a permanent implant, VAS data used for the secondary endpoints will correspond to the results observed at the corresponding collection times (i.e. 1 month, 3 months, 6 months, 9 months, 12 months, 18 months, and 24 months). For subjects who do not have a successful Trial Phase (based on subject's pain score), the VAS data for the secondary endpoints will utilize the results from the end of the Trial Phase.

Subjects who were not able to complete the Trial Phase (e.g., an adverse event experienced during the Trial Phase, physician withdrawal due to non-compliance, withdrawal of consent, etc.) will be removed from the mITT analysis data set as no back VAS pain score is available at the End of Trial visit.

In the event of missing secondary endpoint data the primary analysis of the secondary endpoints will be conducted using multiple imputation instead of the methods specified above. The multiple imputed datasets from the primary endpoint analysis will also be used for the analysis of the secondary endpoints as described in Section 5.7.1.2. The same methods will be used for the responder endpoint evaluation at 1, 3, 9, and 12 months. The evaluation of mean change in VAS at 6 months will estimate the mean change and difference in means between groups along with the associated standard errors which will then be combined across imputations. The imputation model will be extended as needed for the evaluation of the secondary endpoint at 9, 12, 18, and 24 months.

As an additional supporting analysis, likelihood based repeated measures models will be used to produce estimates for the secondary endpoints in the presence of missing data.

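### Trial failures' on-stimulation pain scores are carried to every visit after the leads are removed, which may overstate the test arm's mean VAS improvement

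*SAP*

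**What the plan says.** Protocol B.6.6 sets out the end of the Trial Phase. At that visit "subjects will be assessed for pain intensity under optimal therapy parameters". Success is "defined as a 50% or greater pain reduction from Baseline in their back pain". Subjects who fall short are not implanted: "These subjects will have the leads explanted and will exit the study". No later study VAS is scheduled for them.

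SAP 5.7.1.2 uses these subjects' Trial Phase back pain scores for the primary endpoint and says that the results "will be attributed for each time point throughout the study, as if they remained in the study". SAP 5.7.2.1, whose visit list runs to 24 months, says that for subjects without a successful trial "the VAS data for the secondary endpoints will utilize the results from the end of the Trial Phase".

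SAP 5.7.2 tests mean change in VAS for non-inferiority at 6 months (margin 0.65 cm), then for superiority. Both hypotheses refer to the Primary Efficacy Assessment, which Protocol B.7.2 places at the end of the Trial Phase for trial failures. The repeated-measures comparison of mean change has no hypothesis attached. Protocol B.7.4 lists tests of mean change at every visit; the SAP specifies one at 6 months only.

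SAP 5.2 makes the mITT the primary set and defines it as "All randomized subjects to the test arms who successfully complete the Trial Phase and all successfully randomized subjects to the control arm". SAP 5.3 promises sensitivity analyses for missing data in general terms and names none for trial failures.

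**The concern.** A score obtained during a trial of at most 30 days, with the device delivering its best settings, stands in for up to two years in which the subject has no device. For a responder endpoint this does no harm. For a mean it credits the test arm with whatever partial relief the subject had on stimulation, at every later visit. Because a single fixed value is used, it also adds none of the between-imputation variance that other missing values receive under the multiple imputation in SAP 5.7.1.2.

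At stake are the estimated difference in mean VAS change, the two formal tests of it at 6 months, and the mean-change curves to 24 months. The study's declared success criterion is not at stake.

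**Working it through.** **The plan's own figures.** Protocol B.5.5.1 and SAP 4 give 60% vs 30% responders, two-sided 0.05 and 50 per arm. The Pearson test with pooled variance gives power Φ[(0.30√50 − 1.96√(2 × 0.45 × 0.55)) / √(0.24 + 0.21)] = Φ[(2.121 − 1.379) / 0.671] = Φ(1.107) = 86.6%, which agrees with the stated figure of more than 85%. Randomizing 100 / (1 − 0.33) ≈ 150 also agrees.

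**Responder endpoints.** A trial failure has less than 50% relief by definition. Carrying either the end-of-trial score or baseline gives a non-responder, so responder rates and the 86.6% do not move.

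**Mean change, if pain returns to baseline.** Let f be the share of trial failures in the analysed test arm, r their mean fractional relief at end of trial, and B the mean baseline VAS. Compared with carrying baseline, the rule adds f × r × B to the test-arm mean improvement.

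- f: not given for this study. Protocol B.1 reports that 80% of 20 subjects in the acute feasibility study had at least 50% relief, so 20% is used as a proxy.
- B: entry requires at least 6.0 cm; the mean is not given. Assumed 7.5 cm, range 6 to 9.
- r: not given; it must lie below 50%. Assumed 10% to 40%.

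| f | r | B (cm) | f × r × B (cm) | Share of 0.65 cm |
|---|---|---|---|---|
| 20% | 10% | 7.5 | 0.15 | 23% |
| 20% | 25% | 7.5 | 0.38 | 58% |
| 20% | 40% | 7.5 | 0.60 | 92% |
| 10% | 25% | 7.5 | 0.19 | 29% |
| 30% | 25% | 7.5 | 0.56 | 87% |

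The feasibility study also allows a rough value for r. Its mean relief was 68% with 80% at or above 50%. If percent relief is normal, SD = (68 − 50) / 0.842 = 21.4 points, and mean relief among failures is 68 − 21.4 × 0.280 / 0.20 ≈ 38%. With f = 20% the shift is then 0.46, 0.57 or 0.69 cm for B = 6, 7.5 or 9 cm.

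**Mean change, if failures do as well as CMM subjects.** The reference is now the CMM mean relief c, and the shift is f × (r − c) × B. A 30% responder rate with normal percent relief gives c = 50 − 0.524 × SD. That is 39.5% for an assumed SD of 20 points and 31.6% for 35 points. With f = 20%, B = 7.5 cm and r = 38%, the shift is −0.02 to +0.10 cm. With r = 10% it would be 1.5 × (0.10 − 0.395) = −0.44 cm to 1.5 × (0.10 − 0.316) = −0.32 cm, so the rule would then work against the test arm.

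**Which analysis the rule reaches.** The documents point two ways.

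- Trial failures in the mITT: the Synopsis counts them as non-responders; Protocol B.7.2 gives them a primary assessment; SAP 5.7.1.2 and 5.7.2.1 remove only subjects who did not complete the trial. SAP 5.4 also treats completion and success as separate, counting subjects "completing the Trial phase (with and without success").
- Trial failures out: Protocol B.7.1 and SAP 5.2, read literally, keep only test subjects who complete the Trial Phase successfully.

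On the first reading the rule acts in the primary mean-change analysis. On the second it acts only in the supportive ITT analysis.

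**The case against.** A reader might infer that the rule puts a fixed bias in favour of the test arm into the results. The documents do not support that. No VAS is collected after exit, so neither direction nor size can be shown. The test arm is SCS plus CMM, trial failures continue under the investigator's pain management, and the plan itself expects 30% responders on CMM. Full return to baseline is therefore only one scenario. Against it, Protocol B.3.2 requires at least 6 months of pain refractory to conventional therapy, so a return toward baseline is plausible and is a case the plan never examines.

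A reader might also infer that the SAP already applies the opposite convention to crossover subjects on the same endpoint. It does not. SAP 5.7.2 says that they are "counted as failures (i.e. non-responders) for endpoints defined in terms of responders, carrying forward the baseline (pre-treatment"). That sentence is limited to responder endpoints and sets no explicit rule for crossover subjects' mean change.

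The consequence is bounded. Protocol B.8.2 (Definition of Success) rests success on the responder endpoint alone. Translating 60% vs 30% into means with the same normal model gives (0.253 + 0.524) × SD × 7.5 cm, about 1.2 cm for an SD of 20 points and 2.0 cm for 35. Under those assumptions, removing 0.15 to 0.60 cm would not reverse non-inferiority. The exposure is mainly in the effect estimate.

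Finally, carrying baseline is also a single-value rule, and it may be conservative if failures gain from CMM. That stands, and is why a control-referenced analysis belongs beside it.

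**Conclusion.** The point holds in a limited form. The plan assigns on-stimulation scores to subjects whose leads have been removed, at every visit to 24 months, and names no sensitivity analysis for that choice. Mean VAS change may overstate test-arm improvement by about 0.15 to 0.60 cm if pain returns to baseline, which at the upper end approaches the 0.65 cm margin. If failures do about as well as CMM subjects the effect is close to zero at about 38% carried relief, and it can reverse at lower relief. The failure share, mean baseline, relief among failures and normality are all assumptions. Whether the primary analysis is touched depends on the unresolved mITT membership. This is an inexpensive improvement to a secondary analysis, held with medium confidence.

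**What to change.** 1. In Protocol B.7.1 and SAP 5.2, state whether trial failures belong to the mITT, and make SAP 5.7.1.2 and 5.7.2.1 agree.
2. In SAP 5.7.1.2 and 5.7.2.1, for mean-change analyses only, set the change from baseline of trial failures after lead removal to 0 (baseline carried forward). Name two sensitivity analyses: one using the end-of-trial score as now written, and one imputing from the control arm. Responder status stays non-responder.
3. Align Protocol B.7.2, which fixes the assessment at the end of the Trial Phase, and Protocol B.9.2.4, which repeats the use of Trial Phase results, so that the SAP does not contradict the protocol.

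The cost is a small edit to both documents and a somewhat less favourable test-arm mean change, possibly conservative if failures benefit from CMM. No new data are needed, and sample size and stated power stay as they are.
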